5.6.3 Withdrawal of informed consent

Patients may voluntarily withdraw consent to participate in the study for any reason at any time. Withdrawal of consent from the study is defined as when a patient:

- Does not want to participate in the study anymore, and
- Does not want any further visits or assessments, and
- Does not want any further study related contacts, and
- Does not allow analysis of already obtained biologic material.

In this situation, the investigator must make every effort (e.g. telephone, e-mail, letter) to determine the primary reason for the patient's decision to withdraw his/her consent and record this information.

Study treatment must be discontinued and no further assessments conducted, and the data that would have been collected at subsequent visits will be considered missing.

Further attempts to contact the patient are not allowed unless safety findings require communicating or follow-up.

All efforts should be made to complete the assessments prior to study withdrawal. A final evaluation at the time of the patient's study withdrawal should be made as detailed in the assessment table below.

5.6.4 Lost to follow-up

For patients whose status is unclear because they fail to appear for study visits without stating an intention to discontinue or withdraw, the investigator should show "due diligence" by documenting in the source documents steps taken to contact the patient, e.g. dates of telephone calls, registered letters, etc. A patient cannot be considered as lost to follow-up until the time point of his/her scheduled end of study visit has passed.

5.6.5 Early study termination by the sponsor

The study can be terminated by Novartis at any time for any reason. This may include reasons related to the benefit-risk assessment of participating in the study, practical reasons, or for regulatory or medical reasons (including for example slow enrollment or an unreasonably low number of patients continuing). In the event that the study is terminated early, the IRBs/IECs will be informed. Should this be necessary, the patient must be seen as soon as possible and treated as a prematurely withdrawn patient. The investigator may be informed of additional procedures to be followed in order to ensure that adequate consideration is given to the protection of the patient's interests.

6 Visit schedule and assessments

Table 6-1, Table 6-2, Table 6-3 Table 6-4 and Table 6-5 list all of the assessments and indicate with an "X" when the visits are performed.

Patients must be seen for all visits on the designated day, or as close to it as possible. Missed or rescheduled visits should not lead to automatic discontinuation.

If the **COVID-19 pandemic** limits or prevents on-site study visits, alternative methods of providing continuing care may be implemented. Phone calls, virtual contacts (e.g. teleconsult) or visits by site staff to the patient's home depending on local regulations and capabilities, can replace on-site study visits, for the duration of the pandemic until it is safe for the patient to visit the site again (see Section 6.4 efficacy, Section 6.5.4 Laboratory evaluations, Section 6.5.6 Pregnancy and assessments of fertility, Section 6.6.6 AMG 334 Antibody testing, [REDACTED] Section 7 Safety monitoring and Section 7.6 Prospective suicidality assessment for further COVID-19 guidance related to sample collection).

Table 6-1 Assessment Schedule: Double-Blind Treatment

Epoch	Screen	Baseline ³	Double-Blind Treatment ^{1,4}				Follow-Up ²	Notes	
Visit	1	2	101	102	103	199	301	Follow up visit is 16 weeks after last dose of IMP (V103 / Wk 8), which is 12 weeks after last DBT visit (V199 / Wk 12).	
Week	-6	-4	Day 1	4	8	12/PSD/TD	24/FU		
Obtain Informed Consent	X								
Randomization			X						
Demography	X								
Medical & Medication History	X							Including prior prophylactic migraine medication	
Treatment Failure Confirmation	X								
Complete Physical Exam	S					S	S		
Brief Physical Exam		S	S	S	S				
Height	X								
Weight	X		X			X	X		
Vital Signs ⁵	X	X	X	X	X	X	X		
Chemistry/Hematology	X		X			X	X		
Serum Pregnancy	X					X			
Urine Pregnancy		X	X	X	X		X		
ECG	X		X	X		X			
Anti-AMG Antibodies			X			X	X		
eDiary Dispensing		S							
eDiary Return			S	S	S	S		Pt brings to each visit for use at site	
Clinical Outcomes (eDiary)		Daily (Migraine days, [REDACTED] duration, severity, rescue medication)							

Epoch	Screen	Baseline ³	Double-Blind Treatment ^{1,4}				Follow-Up ²	Notes
Visit	1	2	101	102	103	199	301	Follow up visit is 16 weeks after last dose of IMP (V103 / Wk 8), which is 12 weeks after last DBT visit (V199 / Wk 12).
Week	-6	-4	Day 1	4	8	12/PSD/TD	24/FU	
MPFID (eDiary)			Daily					
C-SSRS	X	X	X	X	X	X	X	Should also be performed at unscheduled visits.
Concomitant Medications	X	X	X	X	X	X	X	
Adverse Events ⁷			X	X	X	X	X	
Serious Adverse Events ⁷	X	X	X	X	X	X	X	
Study Drug Administration ⁸			X	X	X			
Contact IRT ⁹	X	X	X	X	X	X		
Screening Phase Completion Form	X							
Baseline Phase Completion Form		X						
Double Blind Phase Completion form						X		
Follow-Up Phase Completion Form							X	

1 – All study visit target dates are to be calculated from the Day 1 visit date, and all study procedures for a given visit should be completed in the same day.
 
2 – The Follow-Up Visit is required for all patients who either discontinue study drug early or complete the study in either the Double-Blind or Open-Label Treatment Epochs and do not continue commercial drug (if locally available).
 
3 – Enrollment into the Baseline Epoch can occur only if the patient successfully completes all requirements for the Screening Epoch.
								

Table 6-2 Assessment Schedule: Open-Label Treatment– Weeks 13-64 (1st year in Open-Label extension)

Epoch	Open-Label Treatment ^{1,2,3}													
	199	201	202	203	204	205	206	207	208	209	210	211	212	213
Visit														
Week	12	16	20	24	28	32	36	40	44	48	52	56	60	64
Open-label Treatment Phase Entry	X													
Complete Physical Exam	S													S
Brief Physical Exam		S	S	S	S	S	S	S	S	S	S	S	S	
Weight	X			X										X
Vital Signs ⁴	X	X	X	X	X	X	X	X	X	X	X	X	X	X
Chemistry/Hematology	X			X										X
Serum Pregnancy	X													X
Urine Pregnancy		X	X	X	X	X	X	X	X	X	X	X	X	
ECG	X	X												X
Anti-AMG Antibodies	X			X										X
eDiary Dispensing ⁵	S	S	S				S			S			S	
eDiary Return ⁵	S	S	S	S				S			S			S
Clinical Outcomes (eDiary) ⁶	Daily						X			X			X	
MPFID ^{6,9} (eDiary)	Daily						X			X			X	

Epoch	Open-Label Treatment ^{1,2,3}													
Visit	199	201	202	203	204	205	206	207	208	209	210	211	212	213
Week	12	16	20	24	28	32	36	40	44	48	52	56	60	64
C-SSRS	X	X	X	X	X	X	X	X	X	X	X	X	X	X
Concomitant Medications	X	X	X	X	X	X	X	X	X	X	X	X	X	X
Adverse Events ¹⁰	X	X	X	X	X	X	X	X	X	X	X	X	X	X
Serious Adverse Events ¹⁰	X	X	X	X	X	X	X	X	X	X	X	X	X	X
Study Drug Administration ¹¹	X	X	X	X	X	X	X	X	X	X	X	X	X	X
Contact IRT ¹²	X	X	X	X	X	X	X	X	X	X	X	X	X	X

- 1 – All study visit target dates are to be calculated from the Day 1 visit date, and all study procedures for a given visit should be completed in the same day.
 2 – The Follow-Up Visit is required for all patients who either discontinue study drug early or complete the study and do not continue commercial drug (if locally available) in either the Double-Blind or Open-Label Treatment Epochs.
 3 – Entry into the Open-Label Treatment Epoch can occur only if the patient successfully completes all requirements for the Double-Blind Treatment Epoch.
 4 – Includes blood pressure, pulse and temperature.
 5 – eDiaries will be used for the first 12 weeks of the Open-Label Treatment Epoch and again at periodic intervals as identified in the assessment schedule.
 6 - Daily collection during the respective 4 week periods
 7 - HRQ collection after migraines during the respective 4 week periods

10 - SAEs will be collected after signing of the informed consent through the end of the Follow-Up Epoch end of study (16 weeks after the last dose of study drug). Non-serious AEs will be collected after randomization (Visit 101) through the end of the Follow-Up Epoch (16 weeks after the last dose of study drug).

11 – Two pre-filled syringes will be administered by study staff, during the applicable study visits, q.m., s.c..

12 - Sites will access the Interactive Response Technology (IRT) System to enter the patient into the open-label treatment phase and to register study early termination.

X = Assessment to be recorded in the source documents and the clinical data base; S = Assessment to be recorded as source documentation only.

Table 6-5 Assessment Schedule – PTA-Open-Label Treatment

Epoch		PTA Open-Label Treatment						499 ² / End PTA
		Initial 3 month cycle			Repeat 3-Month cycle until end of PTA			
Visit	299	401	402	403	404	405	406	
Weeks	168	172	176	180	184	188	192	
Study drug administration	X	X	X	X	X	X	X	
Contact IRT	X	X	X	X	X	X	X	
Adverse Events/ Serious Adverse Events	X	X	X	X	X	X	X	X
Concomitant medications / therapies	X	X	X	X	X	X	X	X
Clinical Global Impression - Severity	X							
Clinical Global Impression - Improvement		X	X	X	X	X	X	X
Clinical Global Impression – Efficacy Index		X	X	X	X	X	X	X
Pregnancy test (urine) ¹				X			X	X
PTA-Open-Label Treatment Epoch Completion								X

X Assessment to be recorded in the clinical database or received electronically from a vendor

¹ Results of pregnancy tests will be documented in source documents.

² Once PTA ends in a country the patient should come to the clinic for a final End of Treatment visit (occurs 4 weeks after previous dose)

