5.1 Study treatment

5.1.1 Investigational and control drugs

Novartis will supply the investigational product listed below

- AMG 334 70 mg/1 mL pre-filled syringe
- Matching placebo in 1mL pre-filled syringe, identical in appearance

The matching placebo to AMG 334 pre-filled syringe will have the same appearance as the investigational drug. Each syringe will be packaged individually in double blinded fashion for the double-blind treatment epoch and in the open-label fashion for open-label treatment epoch and PTA-Open-Label Treatment Epoch. The study treatments will be labeled as:

- AMG 334 70mg/1mL / Placebo for Double-Blind Treatment Epoch
- AMG 334 70mg/1mL for Open-Label Treatment Epochs. If and when 140 mg/mL pre-filled syringes become available during the Open-Label Treatment Epoch, the 140 mg dose may be administered by a single 140 mg/mL s.c. injection.

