5.5.2 Dispensing the study drug

Each study site will be supplied with study drug in packaging of identical appearance.

Each box of study drug has a 2-part label. A unique medication number is printed on each part of this label which corresponds to one of the 2 treatment arms. Investigator staff will identify the two study drug packages to dispense to the patient by contacting the IRT and obtaining the medication numbers. Immediately before dispensing the packages to the patient, investigator staff will detach the outer part of the label from both of the packages and affix them to the source document (Drug Label Form) for that patient's unique patient number.

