5.5.4 Instructions for prescribing and taking study treatment

Subcutaneous (s.c.) injections are to be given for each investigational product administration. For purposes of study treatment dosing, “q.m.” refers to an every 4 weeks injection regimen. The study drug administration date should be in 4 week increments (+/- 5 days) from the first dose of study drug. Any dose administrations that may occur greater than +/- 5 days from the 4 week time point (e.g., patient unavailability) should be discussed with the Sponsor prior to dosing. The anatomical sites for administration of investigational product are the upper arm, upper thigh, or abdomen; the location of the injection sites should be documented in the source document.

Double-Blind Treatment Epoch:

Two injections of AMG 334 70 mg (equaling 140 mg total dose) or placebo will be administered by qualified study staff at each dosing visit during the 12-week double-blind treatment epoch (i.e., at Day 1 and Weeks 4 and 8).

Open-label Treatment Epoch and PTA-Open-Label Treatment Epoch:

Two injections of open-label AMG 334 70 mg (equaling 140 mg total dose) will be administered by qualified study staff at each dosing visit during the 156-week open-label treatment epoch (ie, at Weeks 12, 16, 20, 24, etc.) and during the PTA-Open-Label Treatment Epoch (ie, at Weeks 168, 172, 176, 180 etc.). If and when 140 mg/mL pre-filled syringes become available during the Open-Label Treatment Epoch, the 140 mg dose may be administered by a single 140 mg/mL s.c. injection.

The investigational product dose is fixed and will not be adjusted for individual patients during the study. There are no temporal restrictions for study drug administration (e.g., proximity to meals, sleep or activity).

All kits of study treatment assigned will be recorded in the IRT. Novartis monitors will reconcile treatment assigned vs treatment administered and ensure that the information is congruent during their monitoring visits.

During the **COVID-19 pandemic** that limits or prevents on-site study visits, delivery of study drug directly to a patient’s home is generally permitted in the event the Investigator has decided that an on-site visit by the patient is no longer appropriate or possible, and that it is in the interest of the patient’s health to administer (e.g., self-injection or study staff administration at patients’

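### Table 6-2 footnote 11 and Section 5.5.2 give a count of two with no strength, which conflicts with the single 140 mg/mL injection that Sections 5.1.1 and 5.5.4 allow in open-label treatment

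*Protocol*

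**What the plan says.** Four places in the protocol bear on how many syringes are used at an open-label visit.

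- **Section 5.5.4 (dosing instructions).** "Two injections of open-label AMG 334 70 mg (equaling 140 mg total dose) will be administered by qualified study staff at each dosing visit". The section then adds a conditional alternative: "If and when 140 mg/mL pre-filled syringes become available during the Open-Label Treatment Epoch", one injection of that strength may replace the two. It also says "The investigational product dose is fixed and will not be adjusted for individual patients during the study".
- **Section 5.1.1 (supply and labels).** The supply list at the top names "AMG 334 70 mg/1 mL pre-filled syringe" and matching placebo. The open-label label bullet further down goes on to say that, once the stronger syringe is available, "the 140 mg dose may be administered by a single 140 mg/mL s.c. injection". The section also says that syringes are packed individually.
- **Table 6-2, footnote 11 (open-label schedule, Weeks 12 to 64).** "Two pre-filled syringes will be administered by study staff, during the applicable study visits". No strength is given and no alternative is mentioned.
- **Section 5.5.2 (dispensing).** "Investigator staff will identify the two study drug packages to dispense to the patient by contacting the IRT and obtaining the medication numbers". Again there is no strength and no alternative. The surrounding text on identical packaging and two treatment arms reads as double-blind wording, but the section is not limited to that epoch.

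**The concern.** The dosing text makes the number of syringes depend on strength. The schedule footnote and the dispensing text fix the number at two whatever the strength. If 140 mg/mL stock reaches a site, one part of the protocol gives a count of one and two other parts give a count of two for the same visit.

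The Amendment 3 change log suggests how this arose. It records the 140 mg/mL option as an addition to Section 5.1.1. For the Week 64 schedule it records only a change to one visit, and it does not list Section 5.5.2.

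At stake is agreement between the dose given and the dose the protocol calls fixed. If the two diverged at some visits, patients would be exposed above the stated total, and long-term safety summaries that describe exposure as 140 mg every four weeks would be wrong for those visits.

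**Working it through.** **Inputs**

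- Stated total per open-label visit: 140 mg (Section 5.5.4).
- Strengths: 70 mg in 1 mL (Section 5.1.1) and 140 mg/mL (Sections 5.1.1 and 5.5.4).
- Fill volume of the 140 mg/mL syringe: not given. I assume 1 mL, because the protocol says one injection delivers 140 mg, and 140 mg / 140 mg/mL = 1 mL.
- Counts: two at 70 mg, or one at 140 mg/mL (Sections 5.1.1 and 5.5.4); two with no strength (footnote 11 and Section 5.5.2).
- Syringes per package: one (Section 5.1.1).

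**Formula:** dose = number of syringes x strength x fill volume.

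| Text followed | Calculation | Total |
|---|---|---|
| 5.5.4, two 70 mg injections | 2 x 70 mg/mL x 1 mL | 140 mg, reproduces the stated total |
| 5.1.1 and 5.5.4, one 140 mg/mL injection | 1 x 140 mg/mL x 1 mL | 140 mg, agrees |
| Footnote 11 count with 70 mg syringes | 2 x 70 mg/mL x 1 mL | 140 mg, agrees |
| Footnote 11 count with 140 mg/mL syringes | 2 x 140 mg/mL x 1 mL | 280 mg, 280/140 = 2.0 times the stated total |

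Three of the four combinations agree with the protocol. Only the last does not, and it requires disregarding the single-injection wording.

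**Could footnote 11 and the option apply to the same visit?** The SAP introduction dates the third amended protocol 8 March 2018. The Amendment 3 text gives first screening on 20 March 2017 and completed enrollment on 6 July 2017.

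- Earliest patient: 20 March 2017 plus 4 baseline weeks gives Day 1 on 17 April 2017. By 8 March 2018 that is 325 days, or 46.4 weeks. Table 6-2 doses left: Weeks 48 to 64, (64 - 48)/4 + 1 = 5.
- Latest patient, if 6 July 2017 is the randomization date: 245 days, or 35 weeks. Doses left: Weeks 36 to 64, (64 - 36)/4 + 1 = 8.
- Latest patient, if 6 July 2017 is the consent date and 6 weeks of screening and baseline follow: 203 days, or 29 weeks. Doses left: Weeks 32 to 64, (64 - 32)/4 + 1 = 9.

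So a continuing patient had at most 5 to 9 Table 6-2 doses left when the option was written. The Amendment 3 text reports 212 patients ongoing at its finalization. These are ceilings: approval took further time, and the documents do not say when, or whether, the stronger syringe arrived.

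**The case against.** The strongest reply is that Section 5.5.4 is the dosing section and is already clear. It gives a count for each strength, both counts give 140 mg, and the dose is said to be fixed. Footnote 11 is a note to a visit table. Section 5.5.2 has staff obtain medication numbers from the IRT, so sites do not pick kits by count. Section 5.5.4 has assigned kits recorded in the IRT and has monitors compare treatment assigned with treatment administered. Section 7.4 captures treatment errors in the dose administration record. The switch is also conditional.

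Most of this stands, and it limits the risk. It does not remove the contradiction. The protocol states no order of precedence between the dosing section and the schedule. Comparing assigned with administered treatment would not reveal a wrong count if the assignment itself were built on two packages per visit. The documents do not describe how the IRT was configured.

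A reader might go further in three ways that the documents do not support.

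- **That the label text covers only the 70 mg syringe in open-label use.** The open-label label bullet in Section 5.1.1 continues to the 140 mg/mL syringe. Only the supply list above it omits that strength.
- **That home self-injection during the pandemic compounds footnote 11.** That text came with Amendment 4, which cites a February 2020 Investigator Brochure. On the latest dating above, Day 1 is 17 August 2017 and Week 64 falls on 8 November 2018. Patients on schedule had left Table 6-2 by then.
- **That the IRT or dose record cannot capture strength.** Their fields are not listed, so this cannot be shown either way.

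**Conclusion.** The inconsistency is real and narrow. For the 140 mg/mL syringe, footnote 11 and Section 5.5.2 give a count that contradicts Sections 5.1.1 and 5.5.4. Footnote 11 is the firmer of the two, since Section 5.5.2 concerns dispensing and is worded for the double-blind epoch.

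A reader might infer that following the protocol as written delivers 280 mg. It does not: a site following Sections 5.1.1 and 5.5.4 gives one syringe and 140 mg. The 280 mg figure rests on the assumed 1 mL fill and on applying the count of two against the single-injection wording. Nor do the documents show that such an error would cause harm. Section 3.3 reports dosing up to 280 mg in healthy volunteers without a difference in safety profile, although it also calls constipation potentially dose-related.

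The conflict should not be extended to all open-label doses. Table 6-2 stops at Week 64, Tables 6-3 and 6-4 are not in the supplied text, and the supplied Table 6-5 text has no syringe count. The primary and secondary double-blind analyses are untouched, because the option applies only to open-label treatment.

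The point is still worth correcting: the conflict sits in an instruction used at dosing visits and would affect patient safety if misread.

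**What to change.** Reconcile these places with the dosing text in Sections 5.1.1 and 5.5.4:

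- Table 6-2 footnote 11;
- any matching footnotes in Tables 6-3 and 6-4, to be checked in the full protocol;
- the package count in Section 5.5.2, either by limiting it to the double-blind epoch or by stating it per strength;
- the supply list in Section 5.1.1, which omits the 140 mg/mL syringe mentioned later in the same section.

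After the change, every syringe or package count should be tied to a labelled strength and agree with the total dose the protocol already states. No new dose or dosing rule is proposed.

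The sponsor should also confirm that existing IRT and dose administration records show strength and number of syringes for each open-label dose, so that the open-label exposure summary can be verified.

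The cost is a few words in one or more footnotes and two sections, plus one records check. It needs no extra patients, visits or analyses.

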6.1 Information to be collected on screening failures

All patients who have signed informed consent but not entered into the Double-Blind Treatment Epoch will have the Screening Phase Disposition and the Baseline Phase Completion eCRF (as applicable), demographics, inclusion/exclusion, and serious adverse event (SAE) data collected. Adverse events that are not SAEs will be followed by the investigator and collected only in the source data.

6.2 Patient demographics/other baseline characteristics

Patient demographic and baseline characteristic data will be collected on all patients include: date of birth, age, sex, race, ethnicity, source of patient referral, relevant medical history/current medical condition present before signing informed consent where possible, diagnoses and not symptoms will be recorded.

Prior headache characteristics and previous headache medication history, including information on the suitability for migraine prophylactics will be collected as part of baseline characteristics.

Investigators will have the discretion to record abnormal test findings on the medical history eCRF whenever in their judgment, the test abnormality occurred prior to the informed consent signature.

6.2.1 Treatment failure confirmation

Confirmation of eligibility related to treatment failure inclusion criteria will be confirmed via the eDiary prior to entry into the Baseline Epoch.

6.3 Treatment exposure and compliance

Study medication is administered by the investigator or designated study staff at each visit. This information should be captured in the source document and the eCRF at each visit. All study treatment dispensed and returned must be recorded in the Drug Accountability Log. Site staff will review eDiary compliance with the patient at each visit, when applicable.

